4.3.2 Gastrointestinal irAEs

Rule out non-inflammatory causes. If non-inflammatory cause is identified, treat accordingly and continue therapy. Opiates/narcotics may mask symptoms of perforation. Infliximab should not be used in cases of perforation or sepsis (Table 4).

Table 4: Gastrointestinal irAEs Management Algorithm

Gastrointestinal irAEs							
CTCAE Grade of Diarrhea/Colitis	Management	Follow-Up					
Grade 1 Diarrhea: <4 stools/day over baseline. Colitis: asymptomatic.	 Continue AGEN1884 therapy per protocol. Symptomatic treatment. 	 Close monitoring for worsening symptoms. Educate subject to report worsening immediately. Consider symptomatic treatment including hydration, electrolyte replacement, dietary changes (e.g., American Dietetic Association colitis diet), and loperamide. If worsens: Treat as grade 2 or 3-4. 					
Grade 2 Diarrhea: 4-6 stools per day over baseline; IV fluids indicated <24 h; not interfering with activities of daily living (ADL). Colitis: abdominal pain; blood in stool.	 Delay AGEN1884 therapy per protocol. Symptomatic treatment. 	 If improves to grade 1: Resume AGEN1884 therapy per protocol. If persists >5 to 7 days or recurs: 0.5-1 mg/kg/day methylprednisolone or equivalent. When symptoms improve to grade 1, taper corticosteroids over ≥1 month; consider prophylactic antibiotics for opportunistic infections; resume AGEN1884 therapy per protocol. If worsens or persists >3 to 5 days with oral corticosteroids: Treat as grade 3-4. 					
Grade 3-4 Diarrhea (grade 3): ≥7 stools per day over baseline; incontinence; IV fluids ≥24 h; interfering with ADL. Colitis (grade 3): severe abdominal pain, medical intervention indicated, peritoneal signs. Grade 4: life-threatening, perforation	 Discontinue AGEN1884 therapy per protocol. 1-2 mg/kg/day methylprednisolone IV or equivalent. Add prophylactic antibiotics for opportunistic infections. Consider lower endoscopy. 	 If improves: Continue corticosteroids until grade 1, then taper over ≥1 month. If persists >3 to 5 days, or recurs after improvement: Add infliximab 5 mg/kg (if no contraindication). Note: Infliximab should not be used in cases of perforation or sepsis. 					

ADL: activities of daily living; CTCAE: Common Terminology Criteria for Adverse Events; h: hour; irAE: immune-related adverse event; IV: intravenous; kg: kilogram; mg: milligram.

Confidential Page 39 of 78

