4.3.3 Pulmonary irAEs

Rule out non-inflammatory causes. If non-inflammatory cause is identified, treat accordingly and continue therapy per protocol. Evaluate with imaging and pulmonary consultation (Table 5).

Table 5: Pulmonary ir AE Management Algorithm

Pulmonary irAEs											
CTCAE Grade of Pneumonitis	Management	Follow-Up									
Grade 1 Radiographic changes only.	 Consider delay of AGEN1884 therapy per protocol. Monitor for symptoms every 2-3 days. Consider pulmonary and infectious disease consults. 	 Re-image every ≥3 weeks. If worsens: Treat as grade 2 or grade 3-4. 									
Grade 2 Mild to moderate new symptoms	 Delay AGEN1884 therapy per protocol. Pulmonary and infectious disease consults. Monitor symptoms daily; consider hospitalization. 1 mg/kg/day methylprednisolone IV or oral equivalent. Consider bronchoscopy, lung biopsy. 	 Re-image every 1-3 days. If improves: When symptoms return to near baseline, taper corticosteroids over ≥1 month, then resume AGEN1884 therapy per protocol, and consider prophylactic antibiotics. If not improving after 2 weeks or worsening: Treat as grade 3-4. 									
Grade 3-4 Severe new symptoms; new/ worsening hypoxia; life- threatening.	 Discontinue AGEN1884 therapy per protocol. Hospitalize. Pulmonary and infectious disease consults. 2-4 mg/kg/day methylprednisolone IV or IV equivalent. Add prophylactic antibiotics for opportunistic infections. Consider bronchoscopy, lung biopsy. 	 If improves to baseline: Taper corticosteroids over ≥6 weeks. If not improving after 48 hours or worsening: Add additional immunosuppression (e.g., infliximab, cyclophosphamide, IV immunoglobulin, mycophenolate mofetil). 									

CTCAE: Common Terminology Criteria for Adverse Events; irAE: immune-related adverse event; IV: intravenous; kg: kilogram; mg: milligram

Confidential Page 40 of 78

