4.3.4 Hepatic irAEs

Rule out non-inflammatory causes (e.g., alcohol use, acute viral hepatitis, flare up from chronic hepatitis, co-infection [e.g., with hepatitis D], etc.). If a non-inflammatory cause is identified, treat accordingly and continue therapy per protocol. Consider imaging for obstruction and a hepatologist consult (Table 6).

Table 6: Hepatic ir AE Management Algorithm

	Hepatic irAEs										
CTCAE Grade of Liver Test Elevation	Management	Follow-Up									
Grade 1 AST or ALT >ULN to 3 x ULN and/or total bilirubin >ULN to 1.5 x ULN.	Continue AGEN1884 therapy per protocol.	 Continue liver function tests (LFT) monitoring per protocol. If worsens: Treat as grade 2 or grade 3-4. 									
Grade 2 AST or ALT >3 to ≤5 x ULN and/or total bilirubin >1.5 to ≤3 x ULN. If subject has concurrent AST or ALT >3 x ULN and total bilirubin >2 x ULN, discontinue AGEN1884 therapy per protocol (Hy's Law)	 Delay AGEN1884 therapy per protocol. Increase frequency of monitoring to every 3 days. 	If returns to baseline: Resume routine monitoring; resume AGEN1884 therapy per protocol. If elevations persist >5 to 7 days or worsen: 0.5-1 mg/kg/day methylprednisolone IV or oral equivalent. When LFT returns to grade 1 or baseline, taper corticosteroids over ≥1 month, consider prophylactic antibiotics for opportunistic infections, and resume AGEN1884 therapy per protocol.									
Grade 3-4 AST or ALT >5 x ULN and/or total bilirubin >3 x ULN.	 Permanently discontinue AGEN1884 therapy per protocol. Increase frequency of monitoring to every 1-2 days. 1-2 mg/kg/day methylprednisolone IV or oral equivalent.* Add prophylactic antibiotics for opportunistic infections. Consult gastroenterology. Consider obtaining MRI/CT scan of liver and liver biopsy if clinically warranted. 	 If returns to grade 2: Taper corticosteroids around 4 to 6 weeks. If does not improve in >3 to 5 days, worsens, or rebounds: Add mycophenolate mofetil 1 g twice daily. If no response within an additional 3-5 days, consider other immunosuppressants per local guidelines. 									

Confidential Page 41 of 78

	Hepatic irAEs	
CTCAE Grade of Liver Test Elevation	Management	Follow-Up

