4.3.5 Endocrine irAEs

Rule out non-inflammatory causes. If non-inflammatory cause is identified, treat accordingly and continue therapy per protocol. Consider visual field testing, endocrinology consultation, and imaging (Table 7).

Confidential Page 42 of 78

Table 7: Endocrine ir AE Management Algorithm

	Endocrine irAEs										
Endocrine Disorder	Management	Follow-Up									
Asymptomatic TSH abnormality	 Continue AGEN1884 therapy per protocol. If TSH <0.5 x lower limit of normal (LLN) or TSH >2 x ULN, or consistently out of range in 2 subsequent measurements: Include free thyroxine (T4) at subsequent cycles as clinically indicated; consider endocrinology consult. 										
Symptomatic endocrinopathy	 Evaluate endocrine function. Consider pituitary scan. Symptomatic with abnormal lab/pituitary scan: Delay AGEN1884 therapy per protocol; 1-2 mg/kg/day methylprednisolone IV or oral equivalent; initiate appropriate hormone therapy. No abnormal lab/pituitary MRI scan but symptoms persist: Repeat labs in 1-3 weeks, MRI in 1 month. 	 If improves (with or without hormone replacement): Taper corticosteroids over ≥1 month and consider prophylactic antibiotics for opportunistic infections. Resume AGEN1884 therapy per protocol. Subjects with adrenal insufficiency may need to continue corticosteroids with mineralocorticoid component. 									
Suspicion of adrenal crisis (e.g., severe dehydration, hypotension, shock out of proportion to current illness)	 Delay or discontinue AGEN1884 therapy per protocol. Rule out sepsis. Stress dose of IV corticosteroids with mineralocorticoid activity. IV fluids. Consult endocrinologist. If adrenal crisis ruled out, treat as above for symptomatic endocrinopathy. 										

irAE: immune-related adverse event; IV: intravenous; kg: kilogram; LLN: lower limit of normal; mg: milligram; MRI: magnetic resonance imaging; TSH: thyroid stimulating hormone; ULN: upper limit of normal.

Confidential Page 43 of 78

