6.7 Handling of Partial Dates for Medications

When determining prior or concomitant medications, partial start dates of prior and concomitant medications will be assumed to be the earliest possible date consistent with the partial date.

 Medication start dates with a missing day and non-missing month will be assumed to have occurred on the first day of the non-missing month, except for medications occurring in the first month of dosing, in which case the date will be one day before the first day of dosing.

Confidential Page 14 of 30

- Medication start dates with missing day and month will be assumed to have occurred on the first day of the non-missing year (i.e., 1 January), except for medications occurring in the first year of dosing, in which case the date will be the informed consent date.
- For post anti-cancer medications only, if both Month and Day are missing, then the start date will be set to December 31 or the end date of this medication, whichever occurs first.
- For post anti-cancer medications only, if only Day is missing, then the start date will be set to the last day of the month or the end date of this medication, whichever occurs first.
- Medications that are not ongoing and have a medication stop date with a missing day and non-missing month will be assumed to have stopped on the last day of the non-missing month.
- Medications that are not ongoing and have a medication stop date with a missing month will be assumed to have stopped on the last day of the non-missing year (i.e., 31 December).

When imputing start date of a medication ensure that the new imputed date is sensible, i.e., is prior to the end date. If start date and/or end date of a prior/concomitant medication is completely missing, do not impute.

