- **Thyroiditis**: autoimmune thyroiditis, thyroiditis, thyroid acute, thyroiditis chronic, thyroiditis fibrous chronic, thyroiditis subacute, immune-mediated thyroiditis
- Hypophysitis: hypophysitis, lymphocytic hypophysitis, hypopituitarism
- Adrenal insufficiency: Addison's disease, adrenal androgen deficiency, adrenal insufficiency, adrenal suppression, adrenocortical insufficiency acute, glucocorticoid deficiency, hypoaldosteronism, mineralocorticoid deficiency,
- **Diabetes** without prior history: type 1 diabetes mellitus, diabetes mellitus, latent autoimmune diabetes in adults, diabetic ketoacidosis, and hyperosmolar coma
- **Nephritis**: autoimmune nephritis, lupus nephritis, nephritis hemorrhagic, immune-mediated nephritis

Confidential Page 23 of 30

- Rash: pemphigoid, rash, rash erythematous, rash generalized, rash macular, rash maculopapular, rash pruritic, rash papular, immune-mediated dermatitis
- Pruritus: pruritus, pruritus allergic, pruritus generalized
- Other Immune-related AEs: myocarditis, immune-mediated myocarditis, uveitis, immune-mediated uveitis, iritis, vitiligo, psoriasis, myositis, immune-mediated myositis, rheumatoid arthritis, systemic inflammatory response syndrome, sarcoidosis, autoimmune disorder, meningitis, encephalitis, encephalitis autoimmune, immune-mediated encephalitis, encephalopathy, autoimmune encephalopathy, immune-mediated encephalopathy, Guillain-Barre syndrome, myasthenia gravis, demyelination, stomatitis, pancreatitis, autoimmune pancreatitis, pancreatitis acute, immune-mediated pancreatitis, immune-mediated gastritis, lichen planus, colitis ulcerative, Crohn's disease, inflammatory bowel disease, hemolytic anemia, immune-thrombocytopenia, immune thrombocytopenic purpura, aplastic anemia, bicytopenia, pancytopenia, immune-mediated pancytopenia

For each cluster, the analysis will summarize: the total incidence and number of all TEAEs included in the cluster and by severity grade, % of pts who received treatment with pituitary and hypothalamic hormones and analogues, with corticosteroids for systemic use, or with thyroid therapy (concomitant medications in, respectively, H01, H02, or H03 ATC2 groups indicated for AE and started following AE onset but no later than the date of AE resolution or 21 days from AE onset, whichever comes earlier), % leading to dose hold, % leading to drug discontinuation, % resolved, time to onset of first TEAE and duration of all TEAEs and TEAEs of grade ≥ 3.

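### The irAE treatment percentages in SAP 8.6.2 leave out escalation immunosuppressants, late starts and some partly dated starts (minor)

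*SAP*

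**What the plan says.** SAP 8.6.2 defines clusters of immune-mediated events by MedDRA preferred term and follows them over the extended on-treatment period, which SAP 6.4 runs to 90 days after the last dose or the end of the study. For each cluster it reports, among other items, the percentage of patients treated with "pituitary and hypothalamic hormones and analogues, with corticosteroids for systemic use, or with thyroid therapy". A medication counts only if it is in the "H01, H02, or H03 ATC2 groups indicated for AE" and was "started following AE onset but no later than the date of AE resolution or 21 days from AE onset, whichever comes earlier". The SAP gives no reason for the three classes or for the 21 days. The same section makes investigator-reported irAEs the primary irAE analysis and the sponsor's cluster-based definition exploratory.

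The protocol's irAE tables go beyond these three classes. Table 5 (pulmonary) says "Add additional immunosuppression (e.g., infliximab, cyclophosphamide, IV immunoglobulin, mycophenolate mofetil". Table 6 (hepatic) says "Add mycophenolate mofetil 1 g twice daily", and repeats it in the rows for HCC subjects. Table 4 (gastrointestinal) names infliximab, and Table 9 (neurological) names IV immunoglobulin or other immunosuppressive therapy.

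For partial medication start dates, SAP 6.7 uses the first of the month when the day is missing, except in the first month of dosing, "in which case the date will be one day before the first day of dosing". When day and month are both missing in the first year of dosing, it uses the informed consent date.

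**The concern.** The cluster table is the only planned summary that ties treatment to an irAE. The investigator-reported irAE tables carry no treatment column. SAP 8.5.5 tabulates all concomitant medications by ATC level 2 and preferred term, without linking them to an event. If the cluster rule leaves out drugs that the protocol itself calls for, or scores treatment that was given as not given, a reader of the study report has no other summary from which to correct it. At stake is how much treatment these events needed, and how often steroids were not enough, for an antibody whose class toxicity is immune-mediated.

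**Working it through.** The plan gives no figure to reproduce. The check sets the counting rule against the protocol's irAE tables and the SAP's date rules.

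**1. Drug class.** Inputs are the waiting times in Tables 4 to 6, counted from event onset or from reaching the stated grade.
- Infliximab for a grade 3-4 gastrointestinal event: about day 3 to 5.
- Infliximab when escalated from grade 2: (5 to 7) + (3 to 5) + (3 to 5) = day 11 to 17.
- Added pulmonary immunosuppression when escalated from grade 2: 14 days + 48 hours = day 16.
- Mycophenolate for a grade 3-4 hepatic event: day 3 to 5. Other agents 3 to 5 days later: day 6 to 10.

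All of these fall inside 21 days, so timing does not exclude these drugs. Class does: none is a pituitary or hypothalamic hormone, a systemic corticosteroid or a thyroid drug. The same tables give methylprednisolone at grade 3-4 before or alongside escalation, so an escalated patient will usually count under H02. What is lost is the distinction between steroids alone and steroids plus a further agent.

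**2. The 21-day cap.** In Table 7, a patient with persisting symptoms but normal laboratory results and scan has laboratory tests repeated at 1 to 3 weeks (day 7 to 21) and an MRI at one month (day 28 to 31). Hormone therapy follows an abnormal laboratory result or scan. A start prompted by that MRI is 28 − 21 = 7 to 31 − 21 = 10 days past the cap, if onset was recorded when symptoms began.

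Recurrence or rebound is a second route. Tables 3, 4 and 6 provide for treatment at that point, and steroid tapers commonly last a month or more. This lowers the subject-level percentage only if the patient had no earlier qualifying start and the recurrence was not recorded as a new event with its own onset.

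**3. Partial dates.** Suppose the first dose is on the 10th of a month and the event starts on the 20th.
- A steroid with its start day missing in that month is dated the 9th, 11 days before the event, and fails the test.
- If the event's day is also missing, SAP 6.6 dates the event to the first dose, the 10th. The drug then precedes it by one day, always.
- With day and month missing in the first dosing year, the drug is dated to consent, before any on-treatment event.
- In a later month, a missing day becomes the 1st. That precedes an event starting on the 12th of that month (fails) but follows one that started on the 25th of the month before (can pass).

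The only plausibility check in SAP 6.7 is against the medication's own end date.

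**4. Size.** One treated subject scored as untreated lowers a cluster's percentage by 100/n points. The documents give no cluster sizes, so n is assumed.

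| Subjects in cluster (assumed) | Points lost per missed subject |
|---|---|
| 5 | 20 |
| 10 | 10 |
| 20 | 5 |

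The SAP does not state the denominator. If it were all Phase 2 subjects (up to 60), the loss would be 100/60 = 1.7 points.

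**The case against.** Much of the case on the other side stands. The cluster analysis is exploratory. The primary safety endpoint concerns frequency, duration and severity of drug-related events, and protocol 6.4.1 does not list irAE treatment. The SAP names its three classes openly. The immunosuppressants will be visible in the general medication table and listings. The protocol's stated waits before a first steroid course are within the cap (more than 1 to 2 weeks for rash, more than 5 to 7 days for grade 2 gastrointestinal and hepatic events), so it leaves those starts intact. SAP 6.7 introduces its rules for classifying medications as prior or concomitant, so applying them to event linkage is an assumption, although the SAP offers no other medication-date rule.

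A reader might also infer stronger claims that the documents do not support.
- *Thyroid therapy is lost because two repeat TSH tests take 42 days.* The condition "consistently out of range in 2 subsequent measurements" sits in the row for asymptomatic TSH abnormality. It leads to free T4 testing and a possible endocrinology consult, not to thyroid therapy, and is only one of several alternative triggers. The SAP window also runs from AE onset, not from the first abnormal value.
- *Steroid-refractory treatment is 0% by construction.* No such row exists, so no 0% is reported.
- *The share needing systemic treatment is most understated for steroid-refractory events.* Those patients have received steroids, so they normally count.
- *Every partial date in the first year fails.* Only the patterns shown above fail, and a missing day in a later month can pass.

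**Conclusion.** The point holds as a minor one. The cluster summary cannot show escalation beyond steroids. Its cap and, if SAP 6.7 governs the linkage, its date imputation can score AE-indicated treatment as not given. Measured against the share actually treated, the last two gaps push the percentage down. The first removes a category rather than shifting the percentage. The loss is 5 to 20 points per missed subject for clusters of 20 down to 5, which are assumed sizes with patients in the cluster as the denominator. The number missed depends on recorded onset dates and on how often start dates are partial, and the documents allow neither to be estimated. No primary endpoint or efficacy result is affected.

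**What to change.** In SAP 8.6.2, count any start of a medication indicated for the AE from the AE onset date (same day included) to resolution or the end of the extended on-treatment period, whichever is first. Keep the 21-day version as a sensitivity analysis. Add a separate row per cluster for the immunosuppressants named in protocol Tables 4, 5, 6 and 9.

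In SAP 6.7, for a medication whose indication is an AE, impute a partial start date no earlier than that AE's onset, where the recorded date parts allow it.

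The cost is SAP wording and minor programming on data that the current rule already needs: start dates, indications and ATC codes. Clinical care does not change. The drawback is that an occasional late start may be treating a recurrence rather than the original event; the retained 21-day analysis shows how much that matters.

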5.1.4 Final Safety Visit

The mandatory Safety Follow-Up Visit should be conducted for all subjects approximately 90 days after the last dose of study drug or before the initiation of a new antineoplastic treatment, whichever comes first. Subjects with an AE of Grade >1 will be further followed until the resolution of the AE to Grade 0-1 or until beginning of a new antineoplastic therapy, whichever occurs first. Subjects with an ADR ongoing at the Safety Follow-up Visit must be followed up until the ADR resolves, becomes stable, or is considered not clinically significant by the investigator.

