5.8.6.2.2 Serious Adverse Events

All AEs that meet the SAE criteria, occurring from the date of consent, must be recorded on the AE pages of the eCRF and reported by facsimile to Agenus/PrimeVigilance within 24 hours of obtaining knowledge of the event. The facsimile report should include all available information requested on the SAE Report Form.

Email:	
Facsimile:	

The SAE Report Form will include data surrounding the event, e.g., the nature of the symptom(s), time of onset in relation to initiation of therapy, duration, intensity, and whether or not therapy was interrupted or discontinued. The investigator's assessment of the probable cause of the event will also be included. In addition, relevant medical history, concomitant medications, laboratory and diagnostic tests reports, and procedures, as well as all pertinent medical information related to the event, will also be collected.

PrimeVigilance will forward SAE queries directly to the investigator requesting incomplete or missing information. It is the investigator's responsibility to be diligent in providing this information back to PrimeVigilance as soon as it is available. Initial reports of SAEs should never be left on telephone voicemails. Always fax SAE Report Forms and follow up with a telephone call if needed.

If you have any safety-related questions or need to report an SAE, please email:

For reported deaths, the investigator should supply the sponsor and the Institutional Review Board (IRB)/Independent Ethics Committee (IEC) with any additional requested information (e.g., autopsy results, hospital discharge reports, and/or certificates of death) and should be sent as soon as they become available. Any additional information, if collected, will be reported to the sponsor as a follow-up to the initial report.

Confidential Page 59 of 78

All SAEs will be followed until the event has resolved or stabilized, regardless of causality.

It is the responsibility of the principal investigator to report SAEs to their IRB. The investigator should also comply with the applicable regulatory requirement(s) related to the reporting of unexpected serious ADRs to the regulatory authority(ies) and the IRB/IEC.

Deaths occurring during the AE reportable time frame should be reported as SAEs and recorded on the eCRF. The underlying event that resulted in death should be recorded as the verbatim term, with "death" recorded as the outcome of the event.

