4.4 Primary Endpoints

- Safety and tolerability will be assessed by monitoring the frequency, duration, and severity of drug-related adverse events; by completing physical examinations; by evaluating changes in vital signs and electrocardiogram (ECG); through clinical evaluations; and laboratory blood and urine sample evaluations.
- PK parameters to be estimated and reported may include, but may not be limited to, maximum drug concentration at steady-state (C_{max-ss}), minimum drug concentration at steady state (C_{min-ss}), area under the drug concentration-time curve within time span t1 to t2 at steady-state (AUC_{(t1-t2)-ss}), area under the drug concentration-time curve from time of dosing to time of last observation (AUC_(0-t)), area under the drug concentration-time curve

from time of dosing extrapolated to infinity (AUC_(0- ∞)), time to reach maximum drug concentration (t_{max}), terminal elimination rate constant (λ_z), terminal elimination half-life (t½), systemic clearance (CL), and volume of distribution (Vd).

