6.4 Definition of an Extended On-Treatment Period

An extended on-treatment period (follow-up) is defined as the time from the first dose of study treatment through 90 days after the last dose of study treatment or end of the study, whichever

occurs first. This is used for reporting immune-related AEs and cluster terms and also as a sensitivity analysis for reporting all treatment-emergent adverse events.

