6.6 Handling of Partial Dates for Adverse Events

When determining treatment-emergent adverse events (TEAEs), partial dates will be handled as follows.

- If the day of the month is missing, the onset day will be set to the first day of the month unless it is the same month and year as study treatment. In this case, the onset date will be assumed to be the first dose date of treatment.
- If the onset day and month are both missing, the day and month will be assumed to be 1 January, unless the event occurred in the same year as the study treatment. In this case, the event onset will be coded to the first dose date of treatment to conservatively report the event as treatment-emergent.
- A missing onset date will be coded as the first dose date of treatment. If the resulting onset date is after a reported date of resolution, the onset date will be set equal to the date of resolution.
- A partially missing resolution date will be conservatively imputed as the latest date in the range of missing date element(s) (for example 2020-10-31 if the date is 2020-10-UNK), date of last dose + 90 days, day of study discontinuation, or death, whichever comes first.

Data listings will present the partial date as recorded in the electronic case report form (eCRF).

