The median duration of TEAE (in days) will be calculated using Kaplan Meier analysis for all patients and AE included in a cluster. Unresolved AEs or AEs with missing resolution information and date will be treated as censored data with the end of the extended on-treatment period as censoring date.

Death summary table will present reasons for deaths on treatment period, in survival follow-up, and overall.

Death details will also be listed (if applicable) including:

- Number of doses of study drug
- Number of cycles
- Age at death
- Study days relative to first dose date, calculated as (death date first dose date + 1)
- Number of days to death from last dose, calculated as (death date last dose date + 1)
- Precipitating AE (if death is an outcome of AE)
- Immune-related AE (if death is an outcome of irAE per investigator)
- Cause of deaths

The following listings will be provided in Safety Analysis Set:

Confidential Page 24 of 30

- All AEs (with TEAEs flagged)
- Related TEAEs
- Serious TEAEs
- TEAEs leading to treatment discontinuation
- TEAEs leading to death

Adverse events observed between signing the informed consent and first dose of study drug will be listed with negative study days.

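### SAP 6.6 can date an AE resolution before its recorded month, and SAP 8.6.2, read literally, censors AE durations according to outcome, which shortens median duration in immune-mediated clusters with long-lasting events

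*SAP*

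**What the plan says.** SAP 8.6.2 defines the duration summary for the immune-mediated clusters: "The median duration of TEAE (in days) will be calculated using Kaplan Meier analysis for all patients and AE included in a cluster". AEs that are unresolved, or that lack resolution information and date, "will be treated as censored data with the end of the extended on-treatment period as censoring date". SAP 6.4 lets that period run "through 90 days after the last dose of study treatment or end of the study", whichever is first. The SAP does not say how an AE with a complete resolution date after that point enters the analysis.

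SAP 6.6 sets a partial resolution date to the earliest of several dates: the latest date compatible with what was recorded, then "date of last dose + 90 days, day of study discontinuation, or death, whichever comes first". It describes this as conservative.

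The protocol collects outcomes past that point. Under Protocol 5.1.4, subjects with an ADR ongoing at the visit about 90 days after last dose "must be followed up until the ADR resolves, becomes stable, or is considered not clinically significant by the investigator". Protocol 5.8.6.2.2 adds: "All SAEs will be followed until the event has resolved or stabilized, regardless of causality". There are limits. Protocol 5.1.4 follows AEs above Grade 1 to Grade 0-1 "or until beginning of a new antineoplastic therapy, whichever occurs first", and Protocol 5.8.6.2.1 lets follow-up of a non-serious AE stop when the subject leaves the study evaluation period.

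**The concern.** Kaplan-Meier is valid only if the time at which an AE is censored carries no information about when it would resolve. Under the literal text of SAP 8.6.2, whether an AE leaves the risk set at last dose + 90 days (the cap) depends on whether it resolved later. Beyond the cap only AEs already known to resolve remain, so the curve falls too fast.

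SAP 6.6 has a separate fault. An AE recorded as resolved in a month after the cap is given an earlier date that contradicts the record, and it then counts as an observed resolution. For a toxicity duration that is not conservative.

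The outputs at stake are the duration summaries for the immune-mediated clusters. Some of these, such as hypophysitis and adrenal insufficiency, can include long or permanent events. The dates imputed under 6.6 would also feed the first-instance irAE durations that 8.6.2 asks for.

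**Working it through.** The documents give no duration figure to reproduce. The checks below use the SAP rules with assumed data.

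**1. Partial-date cap.** SAP 6.6 itself uses October 2020 with unknown day as its example. Imputed date = earliest of 31 Oct 2020 and last dose + 90 days (death and study discontinuation assumed later). The last-dose dates are assumed.

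| Last dose | Imputed date | Days before 1 Oct |
|---|---|---|
| 16 Apr 2020 | 15 Jul 2020 | 78 |
| 15 Jun 2020 | 13 Sep 2020 | 18 |
| 1 Jul 2020 | 29 Sep 2020 | 2 |
| 20 Jul 2020 | 18 Oct 2020 | none (inside the month) |

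The contradiction arises whenever the whole recorded month lies after the cap.

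**2. Ten-AE example.** Assumed: cap at day 120 after onset; resolutions at days 20, 40, 60 and 150; six AEs documented as ongoing at day 400. S(t) is the product of (1 − d/n) over resolution times, with d resolving among n at risk. Under every rule S(60) = 9/10 × 8/9 × 7/8 = 0.70. After that:

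- Censor at the last documented ongoing date: at day 150, n = 7, so S = 0.70 × 6/7 = 0.60. Median not reached.
- Cut all AEs at day 120: seven censored there, S stays at 0.70. Median not reached.
- SAP 8.6.2 read literally: six censored at day 120, so at day 150 n = 1 and S = 0.70 × 0 = 0. Median 150 days.
- SAP 6.6 cap, if the day-150 resolution has only a month recorded and that month lies wholly after the cap: an event at day 120 with n = 7, so S = 0.60. The median is still not reached, but the curve drops 30 days early, at a time when nothing resolved.

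**3. Simulation.** 400,000 AEs per scenario. Assumed: onset to last dose uniform over 0-63 days; exponential time to resolution among AEs that resolve; follow-up 0-180 days past the cap (0-365 in the row marked *); 20% of resolved AEs partially dated in the last column only. Entries are median days; NR = not reached.

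| Median if resolving; never resolve | True | Last documented date | Common cut | Literal 8.6.2 | Literal + 6.6 rule |
|---|---|---|---|---|---|
| 30; 0% | 30.0 | 30.0 | 30.0 | 30.0 | 33.7 |
| 60; 0% | 59.9 | 59.9 | 59.9 | 59.9 | 63.2 |
| 90; 0% | 89.9 | 89.9 | 89.9 | 89.9 | 92.4 |
| 150; 0% | 149.8 | 149.9 | 150.2 | 134.2 | 129.1 |
| 90; 30% | 163.0 | 163.0 | NR | 137.4 | 132.9 |
| 120; 30%* | 217.0 | 217.3 | NR | 155.6 | 146.6 |
| 60; 45% | 208.2 | 208.2 | NR | 143.6 | 140.0 |
| 90; 45% | 311.4 | 317.4 | NR | 154.3 | 151.2 |
| 60; 60% | NR | NR | NR | 159.1 | 157.4 |

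Two further scenarios with 60% never resolving and the longer follow-up gave 162.8 and 173.6 days under literal 8.6.2, again where the truth is not reached.

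The 6.6 rule acts both ways. It lengthens short AEs, because the latest possible date is imputed, and shortens long ones, because of the cap.

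**4. Opposite direction.** Suppose AE status is lost before the cap in 40% of AEs (assumed), yet they are censored at the cap as though seen ongoing until then. With all other AEs cut at the cap, the median becomes too long: 59.9 becomes 61.9, 89.9 becomes 101.8, and 107.9 becomes 137.2.

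**The case against.** The strongest reply is that right-censoring at last dose + 90 days does not in itself shorten a Kaplan-Meier median. That is correct: the common-cut column is either right or not reached. A reader might take a common cut as the intention, since SAP 8.6.2 speaks of cluster TEAEs evaluated within the extended treatment period and the 6.6 cap ends at the same point. The reading is plausible, but it is not written. The censoring sentence names only unresolved AEs and those with missing outcome, 6.6 caps only partial dates, and 6.10 limits imputation to listed exceptions that do not cover complete dates. Even under a common cut, 6.6 would place a false resolution at the cut.

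Three stronger readings are tempting and should be dropped:

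- **The primary endpoint is biased.** SAP 4.4 refers to "monitoring the frequency, duration, and severity of drug-related adverse events". The Kaplan-Meier rule covers preferred-term immune-mediated clusters regardless of relatedness, and SAP 8.6.2 treats the sponsor's cluster-based irAE definition as exploratory.
- **Persistent toxicity is hidden.** Each cluster summary also gives the percentage resolved and the use of hormone, corticosteroid or thyroid treatment. All AEs are listed, with partial dates shown as recorded.
- **Every ADR is followed to resolution.** Follow-up may end when the ADR is stable or not clinically significant, and a hormone deficiency on replacement could count as stable. How many late resolution dates will exist is unknown.

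It also stands that the cap affects only partial dates falling after last dose + 90 days, and that the planned statistic is the median, which barely moves for short-lived clusters.

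**Conclusion.** Wrong as written, within a limited scope. The 6.6 cap is an error under any reading: it can override a recorded month or year and turn a long AE into a shorter observed one. The 8.6.2 rule is biased on its literal reading and undefined on the most generous one. Under the literal reading the median is too short for clusters with long or permanent events: by roughly 16 days at a true median of 150 (149.8 − 134.2 = 15.6), by about 65 days at 208 (208.2 − 143.6 = 64.6), and a finite median where the truth is not reached. It can be too long where AE status is lost before the cap. The sizes rest on assumed onset, resolution and follow-up patterns; only the directions carry over. The affected outputs are the immune-mediated cluster duration summaries and, through imputed dates, other irAE durations.

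**What to change.** - **SAP 6.6:** remove last dose + 90 days from the cap on partial resolution dates. Impute the latest date consistent with the recorded month or year, never before the first such date (study discontinuation must not override this) and never after death. Query a record that cannot satisfy both.
- **SAP 8.6.2:** state how resolutions after the extended on-treatment period are handled, by one of two rules. Either (a) censor each unresolved AE at the last date it was documented as ongoing and keep later resolutions as events; or (b) cut all AEs at the end of the extended on-treatment period, so that AEs resolving later are censored there too. Under both, an AE whose status was lost earlier is censored when last documented as ongoing, and nothing is censored after death.
- Do not use the last survival contact as the censoring date. Those calls cover survival and new therapy, and the protocol's schedule of assessments has no AE review there.
- Keep the 90-day window for deciding which onsets count.

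The cost is a few sentences and a programming change, with no new visits. Rule (a) needs a last-documented-ongoing date for each AE; check that the eCRF supports one. Reported medians for long-lasting clusters will lengthen or become not reached.
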